16.1.4. SENSITIVITY ANALYSIS OF PRIMARY EFFICACY VARIABLE

- Sensitivity to analysis set: the PP population will be used with the same MMRM model described above to establish non-inferiority. For sensitivity analysis, all non-missing HbA1c data will be used regardless if subject switched their assigned study medication.
- Sensitivity to missing data assumptions:
 - Same analysis approach as the primary analysis, but without imputing missing values. This will be analyzed based in ITT.
 - In another method, the same analysis approach as the primary analysis will be performed, but the imputed values will be corrected such that the full non-inferiority margin will be added for imputed values in Process VI group. This will be analysed based on ITT.
 - In a third sensitivity analysis, tipping-point analysis will be performed using an algorithm proposed by [Yan et al \(2009\)](#) to explore the robustness of the results with regard to a bias against the Process VI treatment arm and in favour of the Process V treatment arm. In order to quantify the bias (k), scenario 2 of the [Yan et al \(2009\)](#) algorithm will be used. Missing Week 18 values will have the value k (positive) added to the Process VI arm (worsening results) and subtracted from the Process V arm (improving results). The value for k is determined by adjusting the bias in an MNAR version of starting with a value of 0.01 and increasing it until the MNAR version of the MI method described in [Appendix 4](#) meets or surpasses the non-inferiority margin. That is the upper limit of 95% interval of treatment difference is ≥ 0.4 (p-value for test non-inferiority is ≥ 0.05). The seed and code for this process are detailed in [Appendix 4](#). The shift parameter as well as summary statistics for the MI model with the tipping point adjustment of k will be reported.
 - As a final sensitivity analysis, missing data will be imputed by using LOCF. An ANCOVA model will be used on the change from baseline in HbA1c to month 18. The model will include treatment (2 levels: MYL-1501D Process V and MYL-1501D Process VI) as fixed effect, the baseline HbA1c as covariate, and patient as random effect. The pooled sites and basal insulin dose time (morning or event) will also be included in the model as fixed effects. This will be analyzed on ITT and PP.
 - In addition, the means for each treatment and difference between treatments for missing data at Week 18 will be summarized for all sensitivity analyses.

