7.1 Sample Size Determination

A total of 202 subjects with T1DM are planned to be randomized for this study and will receive either MYL-1501D Process V product or MYL-1501D Process VI product, in a 1:1 ratio.

The sample size estimation is based on assumptions for the change from baseline up to week 18 in HbA1c with either MYL-1501D product from Process V or Process VI. It is assumed, that true mean groups mean difference is 0.03 and standard deviation is equal to 0.74. To demonstrate non-inferiority margin of 0.4% using a 2-sided 95% confidence interval and a 90% power, a total of 172 subjects (86 subjects per treatment group) are required.

To account for a maximum of 15% of subjects being not eligible for the per protocol analysis, a total sample size of 202 is planned to be randomized for this study. The true treatment difference and standard deviation is based on previous study MYL-GAIA-3001.

No replacement of subject will be performed if subject discontinued prematurely from the study.

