7.5. STATISTICAL TESTS

The default significant level will be (5%); confidence intervals will be 95% and all tests will be two-sided, unless otherwise specified in the description of the analyses.

Non-inferiority will be tested at 2.5% (one-sided) level of significance.

Document: \sasdata\Mylan\Insulin_glargine\SYA22825\Biostatistics\Documentation\SAP\MYL-1501D-3004_SAP_Final_2_0_clean.doc

Author: [name]

Version Number:

2.0

Version Date:

18OCT2018

Template No: CS_TP_BS016 Revision 4
Effective Date: 01Apr2016

Reference: CS_WI_BS005

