Treatment group comparison at week 18 will be based on the least square mean (LS mean) difference between treatment groups (i.e., MYL 1501D Process VI – MYL 1501D Process V) in change from baseline in HbA1c estimated by the model in each imputed datasets. Results from analysis of each imputed dataset i.e., LS mean differences and their standard error (SE), will be combined using the Rubin's imputation rules to produced pooled LS mean estimate of treatment difference and its 2-sided 95% confidence interval (CI).

Non-inferiority will be established if the upper limit of the two sided 95%CI for the difference (MYL-1501D Process VI minus Process V) of mean change from baseline to endpoint for HbA1c is not greater than 0.4% at week 18.

Refer to [APPENDIX 3](#) for SAS code example.

For graphical display at scheduled visits, the LS Means and 2-sided 95% CI for the changes from baseline in HbA1c to week 12 and week 18 obtained from the MMRM model will be presented by treatment group. Similar graphical display will be presented for the mean actual HbA1c values and SD over time by treatment group.

Document:	\sasdata\Mylan\Insulin_glargine\SYA22825\Biostatistics\Documentation\SAP\MYL-1501D-3004_SAP_Final_2_0_clean.doc		
Author:	[name]	Version Number:	2.0
		Version Date:	18OCT2018
Template No:	CS_TP_BS016 Revision 4	Reference:	CS_WI_BS005
Effective Date:	01Apr2016		

Analysis Plan Template

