APPENDIX 4. SAS CODE EXAMPLE FOR TIPPING POINT

```
/*An MNAR version of the MI procedure from Appendix 3 will be used.
The SHIFT value will start at 0.01 and be incremented until the critical
value for non-inferiority of 0.4 is surpassed. In particular, the upper limit
of the 95% confidence interval of the treatment difference will be calculated
for each iteration of the 0.01 increase to the MNAR adjustment and once it
surpasses 0.4, we take that MNAR adjustment value as k. */

/* The first part gives a monotone patern to the data */
/* It imputes the holes in the data but leave empty the missings at the */
/* end for discontinued patients */

Proc mi data= <<insert input dataset name>> out=datamono
  seed=20171220
  NIMPUTE=100;
  by trtp;
  var inv01 inv02 ... inv13 binstime HbA1c_BASE HbA1c_WK12 HbA1c_WK18;
  mcmc impute = monotone chain= multiple;
run;

/* This part gives the imputation at the end of data */
/* Experimental treatment is trtpn=2, control treatment is trtpn=1 */
/* The shifts are done on AVAL not the CHG therefore we subtract */
/* a positive shift to the control making it harder to obtain */
/* non-inferiority and at the same time add a positive shift to the */
/* experimental treatment */

proc sort data=datamono;
  by _imputation_;
run;
```

Document:	\sasdata\Mylan\Insulin_glargine\SYA22825\Biostatistics\Documentation\SAP\MYL-1501D-3004_SAP_Final_2_0_clean.doc		
Author:	[name]	Version Number:	2.0
		Version Date:	18OCT2018

Template No: CS_TP_BS016 Revision 4 Reference: CS_WI_BS005
Effective Date: 01Apr2016

Analysis Plan Template

```
proc mi data = datamono out = datamono2
    seed =20171220
    NIMPUTE=1;
by _imputation_;
    class trtpn strata sitegr1;
    monotone reg;
    MNAR    Adjust (<HbA1c_WK18>/SHIFT= +Kprime ADJUSTOBS=(trtpn='2'))
            Adjust (<HbA1c_WK18>/SHIFT= -Kprime ADJUSTOBS=(trtpn='1'));

    Var trtpn strata sitegr1 HbA1c_BASE HbA1c_WK12 HbA1c_WK18;
;
run;
```

Where Kprime is the shift value starting at 0.01 and ending at k.

```
proc mixed data= <<dataset>> method=REML order=internal;
    by shift_imputation_;
    class trtp(ref="Process V") strata sitegr1 avisit usubjid;
    model change= HbA1c_BASE trtp strata avisit sitegr1 trtp*avisit/DDFM=KR;
    repeated avisit/type=UN subject=usubjid;
    lsmeans trtp*avisit/diffcl;
run;
```

Document: \sasdata\Mylan\Insulin_glargine\SYA22825\Biostatistics\Documentation\SAP\MYL-1501D-3004_SAP_Final_2_0 clean.doc

Author: [name]

Version Number:

2.0

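### In SAP V2.0 section 16.1.4 the p-value threshold in the tipping-point stop rule does not match the confidence-limit rule it restates, given the one-sided 2.5% non-inferiority test in section 7.5

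*SAP*

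**What the plan says.** SAP V2.0 section 16.1.4 describes a tipping-point analysis in which missing Week 18 HbA1c values are made worse by k in the Process VI arm and better by k in the Process V arm. The shift starts at 0.01 and grows until non-inferiority is lost. The stopping point is given in two forms. The first is a confidence limit: "That is the upper limit of 95% interval of treatment difference is ≥ 0.4". The second follows in parentheses as its equivalent: "p-value for test non-inferiority is ≥ 0.05". The parenthesis does not say whether this p-value is one-sided or two-sided. The resulting k is to be reported.

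Three other places bear on the rule:

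- **Section 7.5** gives a general default, "The default significant level will be (5%); confidence intervals will be 95% and all tests will be two-sided, unless otherwise specified", and then an explicit exception: "Non-inferiority will be tested at 2.5% (one-sided) level of significance".
- **Section 16.1.3** decides the primary question on a confidence limit: "Non-inferiority will be established if the upper limit of the two sided 95%CI for the difference" is not above 0.4%.
- **Appendix 4** recomputes the 95% upper limit at each 0.01 step and stops once it "surpasses 0.4, we take that MNAR adjustment value as k". It mentions no p-value.

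**The concern.** The two forms in 16.1.4 are meant to describe one event. Under the test specified in 7.5 they describe two. Non-inferiority at one-sided 2.5% is lost when the one-sided p-value reaches 0.025, which is when the two-sided 95% upper limit reaches 0.4. A one-sided p-value of 0.05 is reached later, when the two-sided 90% upper limit gets to 0.4.

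k is the figure a reader will use to judge how far the missing data could depart from the imputation assumption before the primary conclusion fails. If the search stopped on a one-sided p-value of 0.05, it would run past the point where non-inferiority had already been lost, and the reported k would look more reassuring than it should. The error could go only in that direction. A sensitivity analysis would then be using a more lenient threshold than the analysis it is meant to test.

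**Working it through.** **Inputs**

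- Margin 0.4; "true mean groups mean difference is 0.03 and standard deviation is equal to 0.74" (Protocol version 2.0, section 7.1).
- 202 subjects planned at 1:1, so 101 per arm (same section). The site-pool table in SAP V2.0 section 8.2 sums to 13+9+13+19+16+9+10+12+29+37+13+8+23+8 = 219.
- Shift of +k in Process VI and −k in Process V (SAP 16.1.4).
- *Assumption:* share f of Week 18 values missing in each arm. The current documents give no figure, so 5%, 10% and 15% are shown.
- *Simplifications:* normal quantiles; no extra variance from imputation; no gain from covariate adjustment.

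**Step 1. Which alpha does the design use?**
n per arm = 2 × SD² × (z₁₋α + z₀.₉₀)² / (0.4 − 0.03)².

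- At one-sided 0.025: 2 × 0.74² × (1.960 + 1.282)² / 0.37² ≈ 84.1, so 85. The t-based version gives 86 per arm (172 in total, power 0.903), which is the protocol's figure.
- At one-sided 0.05: 69 per arm, which does not match.
- 172 / 0.85 = 202.4, against 202 planned.

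The design therefore rests on one-sided 0.025, as section 7.5 says.

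**Step 2. Which p-value matches a 95% upper limit of 0.4?**
The upper limit is d + 1.960 × SE, where d is the estimated difference. Setting it to 0.4 gives (0.4 − d)/SE = 1.960. The one-sided p-value is 1 − Φ(1.960) = 0.025, and the two-sided p-value against 0.4 is 0.050. Neither depends on the sample size.

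**Step 3. Where would each rule stop, at 101 per arm?**
SE = 0.74 × √(2/101) = 0.1041.

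| Stop rule | Difference at stopping | 95% upper limit there |
|---|---|---|
| 95% upper limit = 0.4 | 0.4 − 1.960 × 0.1041 = 0.196 | 0.400 |
| One-sided p = 0.05 | 0.4 − 1.645 × 0.1041 = 0.229 | 0.433 |

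The gap is (1.960 − 1.645) × 0.1041 = 0.033.

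**Step 4. What does that do to k?**
The opposing shifts move the difference by about 2 × f × k. Starting from 0.03, k = (difference at stopping − 0.03)/(2f). The ratio of the two k values does not depend on f:

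(0.2287 − 0.03)/(0.1959 − 0.03) = 1.198, an excess of about 20%.

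At N = 219, SE = 0.1000 and the ratio is (0.2355 − 0.03)/(0.2040 − 0.03) = 1.181, about 18%. At N = 172 the excess is about 24%.

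Absolute values at N = 202, in HbA1c percentage points:

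| Missing per arm (assumed) | k, 95% limit rule | k, one-sided p = 0.05 | Excess |
|---|---|---|---|
| 5% | 1.66 | 1.99 | 0.33 |
| 10% | 0.83 | 0.99 | 0.16 |
| 15% | 0.55 | 0.66 | 0.11 |

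**The case against.** The strongest reply is that the operative rule is already settled. Section 16.1.4 puts the confidence limit first and refers to Appendix 4 for the seed and code. Appendix 4 defines k by the 95% limit alone, and its code asks for differences with confidence limits, not a test against 0.4. A programmer who follows Appendix 4 obtains the right k. This stands, and it confines the consequence to the case where someone implements the parenthesis. It does not remove that case entirely: the stopping rule in Appendix 4 is a comment, and the code shown ends at the mixed model, with no pooling step and no stopping logic. The stop has to be programmed from text, and 16.1.4 offers two thresholds.

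A second reply is that the p-value may be meant as two-sided. A two-sided p-value against 0.4 is exactly 0.05 when the 95% limit is 0.4, so the two forms would then agree. This is a possible reading, since two-sided is the SAP's default. But the parenthesis names the non-inferiority test, for which 7.5 makes an explicit one-sided exception, and the reader is left to guess that the exception does not apply.

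Third, the size is hypothetical. The missing shares are assumed, and the absolute excess is largest where k is already several times the margin (1.66 against 1.99 at 5% missing). None of the calculated cases shows the robustness conclusion reversing. This also stands.

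A reader might infer that the reported k will be overstated, or that the primary test is run at the wrong level. The documents support neither. Appendix 4 gives the correct stop, and sections 7.5 and 16.1.3 and the protocol's sample size all agree on one-sided 0.025.

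**Conclusion.** The threshold in the parenthesis is wrong under the SAP's own one-sided test: it should be 0.025. Its effect on k is conditional. k is overstated only if a one-sided p-value of 0.05 is used to stop the search. The overstatement would then be about 20% at 101 per arm, or about 18% at 219 subjects, given SD 0.74, a starting difference of 0.03 and no added imputation variance. In absolute terms it would be roughly 0.1 to 0.3 HbA1c points for assumed missing shares of 15% down to 5% per arm. The mismatch in wording is certain on the one-sided reading; an error in the reported figure is only possible. It is worth correcting because k is a reported robustness figure with two competing stop thresholds, and choosing between them after unblinding would be post hoc.

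**What to change.** In SAP section 16.1.4, either delete the parenthesis so that only the 95% upper limit decides, or replace its content with *one-sided p-value for non-inferiority ≥ 0.025*. Deletion is the simpler choice, because Appendix 4 needs no p-value. Both options bring 16.1.4 into line with 7.5, 16.1.3 and Appendix 4, which need no change on this point.

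The cost is one phrase, with no effect on data collection, the primary analysis or the sample size. If the program already follows Appendix 4, k does not change.

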16.2. SECONDARY EFFICACY

The secondary efficacy analyses will be performed for the ITT population.

16.2.1. SECONDARY EFFICACY VARIABLES & DERIVATIONS

16.2.1.1. Fasting plasma glucose

The fasting plasma glucose is collected at baseline, week 2 (visit 8), week 6 (visit 10), week 12 (visit

Document:	\sasdata\Mylan\Insulin_glargine\SYA22825\Biostatistics\Documentation\SAP\MYL-1501D-3004_SAP_Final_2_0_clean.doc		
Author:	[name]	Version Number:	2.0
		Version Date:	18OCT2018
Template No:	CS_TP_BS016 Revision 4	Reference:	CS_WI_BS005
Effective Date:	01Apr2016		

Analysis Plan Template

12) and week 18 (visit 14, End of Treatment). The measurements are performed by the central laboratory Q2.

Actual values and changes from baseline at each time point will be computed and summarized by treatment group.

A separate analysis will be performed excluding patients with no fasting status.

16.2.1.2. Daily insulin dose per unit body weight (mealtime, basal insulin and total) for days of 8-point profiles

Patients will be asked to document the dose of insulin taken on the same day they will perform the 8-point SMBG profiles (from week -3 to week 18). The measurements are taken the week prior to the visits, so the week prior to:

- Week -3 (Visit 3)
- Week -2 (Visit 4)
- Week -1 (Visit 5)
- Week 0 (Visit 6)
- Week 6 (Visit 10)
- Week 12 (Visit 12)
- Week 18 (Visit 14)

Doses will be recorded in the patient's diary. This data will be transcribed to the eCRF after the patient diary is collected, by the investigator or designee at scheduled visits. The patient should document the 3 pre-visit estimations in the diary; and will be advised to document any additional estimations.

There will be three doses variables: meal time insulin dose, basal insulin and total insulin dose.

Daily Meal time insulin dose: is the sum of all the total daily meal time insulin (Humalog) dose over the double-blind treatment period divided by the number of days measured. For the computation of total daily mealtime doses, only the patients with at least three mealtime doses at a particular day are considered. That is, total daily mealtime dose will not be computed for a day if the mealtime dose is recorded less than 3 times for that day.

Daily Basal insulin dose: is the average of the insulin dose over days measured during the double-blind period.

Daily Total insulin: is the sum of all total daily meal time doses and all basal insulin doses over the double-blind treatment period divided by the number of days measured. Similarly to total daily mealtime dose for which less than 3 mealtime doses are recorded, the missing insulin doses will not be considered for the average computation. That is, if either the mealtime doses are recorded less than 3 times or the basal insulin dose is missing for a particular day of collection, total insulin dose will not be computed. The total insulin dose will be computed for the remaining days where basal insulin dose and at least 3 mealtime doses are collected.

All doses will be divided by total body weight (kg) to convert to daily insulin dose (U) per unit body weight (kg). If body weight at that visit is missing, the weight from previous visit will be used.

Document:	\\sasdata\Mylan\Insulin_glargine\SYA22825\Biostatistics\Documentation\SAP\MYL-1501D-3004_SAP_Final_2_0_clean.doc		
Author:	[name]	Version Number:	2.0
		Version Date:	18OCT2018
Template No:	CS_TP_BS016 Revision 4	Reference:	CS_WI_BS005
Effective Date:	01Apr2016		

Analysis Plan Template

16.2.1.3. 8-point Self-Monitored Blood Glucose (SMBG) profile

8-point SMBG profile measurements will be performed by the patient at home and recorded in the patient diary. A single 8-point SMBG profile set includes measurements of SMBG values on 3 days, performed in the week preceding the next visit (of the 3 days, 2 should be consecutive). The patient should document the 3 pre-visit measurements in the diary.

The following summaries will be summarized at week 6, 12, and week 18:

Individual 8-points SMBG:

The over 3 day averages will be performed for the measures taken at:

- Before breakfast
- Two hours after breakfast
- Before lunch
- Two hours after lunch
- Before dinner
- Two hours after dinner
- Just before sleep
- At 3:00 AM

Averages will be performed at each visit.

Excursions and averages in SMBG:

The following averages will be computed:

- Morning excursion
- Noon excursion
- Evening excursion
- Overall excursion
- Pre-meal average
- Post-meal average
- (4-point average) pre-meal and bedtime average
- Overall average

The individual excursion values will be obtained by subtracting post-meal values with pre-meal values, it will be applicable for morning excursion, noon excursion and evening excursion on the respective days. For the overall excursion at morning, afternoon and evening, the individual excursion values obtained on each day will be averaged across the three days.

To compute the overall excursion, first the average of the morning, noon and evening excursion within a day will be computed, then the average will be done across the 3 days.

Document:	\sasdata\Mylan\Insulin_glargine\SYA22825\Biostatistics\Documentation\SAP\MYL-1501D-3004_SAP_Final_2_0_clean.doc		
Author:	[name]	Version Number:	2.0
		Version Date:	18OCT2018
Template No:	CS_TP_BS016 Revision 4	Reference:	CS_WI_BS005
Effective Date:	01Apr2016		

Analysis Plan Template

The pre-meal average will be the average of the following timepoints: before breakfast, before lunch, before dinner on each day, then the average will be done over the 3 days.

The post-meal average will be the average of the following timepoints: two hours after breakfast, two hours after lunch, two hours after dinner on each day, then the average will be done over the 3 days.

The pre-meal and bedtime average will be the average of the following timepoints: before breakfast, before lunch, before dinner, just before sleep, then the average will be done over the 3 days.

The overall average will be the average of all the 8 timepoints during a day. The daily average will not be computed for a day if more than 3 timepoints are missing on a particular day. The overall average will be kept missing if the daily average is missing for all three days. If the average is missing for one or two days, the average of the remaining days will be considered for the computation.

16.2.2. MISSING DATA METHODS FOR SECONDARY EFFICACY VARIABLE(S)

Imputation will be performed for the SMBG and weight for dose calculation as described in [section 16.2.1](#).

16.2.3. ANALYSIS OF SECONDARY EFFICACY VARIABLES

16.2.3.1. Analysis of change from baseline in HbA1c at scheduled visits

Descriptive statistics will be presented for actual and change from baseline to scheduled visits for HbA1c.

Treatment group comparison will be done using the MMRM model as used for the primary endpoint (without imputing the missing values), including treatment, visit, treatment-by-visit interaction, pooled-investigator, basal insulin dosing time, as fixed effects, baseline values as covariate and subjects as random effect.

LSMeans for each treatment group, as well as associated SE and 2-sided 95% CI will be provided by visit. Differences in LSMeans will be calculated and associated 2-sided 95% confidence intervals and p-values will be provided for each visit.

16.2.3.2. Analysis of change from baseline in fasting plasma glucose

Descriptive statistics will be presented for actual and change from baseline to scheduled visits for fasting plasma glucose. A separate analysis will be done with excluding data with non-fasting status.

Treatment group comparison will be done using the MMRM model as used for the primary endpoint (without imputing missing values), including treatment, visit, treatment-by-visit interaction, pooled-site, basal insulin dosing time, as fixed effects, baseline values as covariate and subjects as random effect.

LSMeans for each treatment group, as well as associated SE and 2-sided 95% CI will be provided by visit. Differences in LSMeans will be calculated and associated 2-sided 95% confidence intervals and p-values will be provided for each visit.

For graphical display at scheduled visits the mean and SD plot will be prepared for the actual plasma

Document: \sasdata\Mylan\Insulin_glargine\SYA22825\Biostatistics\Documentation\SAP\MYL-1501D-3004_SAP_Final_2_0_clean.doc

Author: [name]

Version Number:

2.0

Version Date:

18OCT2018

Template No: CS_TP_BS016 Revision 4

Reference: CS_WI_BS005

Effective Date: 01Apr2016

Analysis Plan Template

glucose measurement by visit and treatment group; LSMeans and 2-sided 95% CI from the same MMRM model will similarly be displayed graphically.

16.2.3.3. Analysis of Change in Daily insulin dose per unit body weight (mealtime, basal insulin and total) for days of 8-point profiles.

Descriptive statistics will be tabulated by treatment and by timepoint. Change from baseline to post-baseline timepoints will also be presented for insulin dose including daily basal insulin dose, daily meal time insulin dose, and daily total insulin dose.

These secondary efficacy parameters will be analyzed using the same MMRM model as the primary efficacy analysis (without imputing missing values). Estimates of the means, LSMeans (2-sided 95% CIs) as well as treatment difference at each visit will be presented.

A graphical display at scheduled visits with the mean and SD plot will be prepared for each of these secondary efficacy endpoints by visit and treatment group; LSMeans and 2-sided 95% CI from the same MMRM model will similarly be displayed graphically.

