3.2.2 Secondary Endpoints

3.2.2.1 Efficacy

- Change in fasting plasma glucose from baseline
- Change in basal insulin, meal-time, and total insulin dose per unit body weight (U/kg) from baseline
- Change in 8-point SMBG profile from baseline

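### The main fasting plasma glucose analysis is not limited to fasting samples, and the SAP defines the fasting-only analysis in two ways that do not agree

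*SAP*

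**What the plan says.** The protocol lists "Change in fasting plasma glucose from baseline" among the secondary efficacy endpoints (section 3.2.2.1). SAP V2.0 carries it out in two places.

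- Section 16.2.1.1 (derivations): "Actual values and changes from baseline at each time point will be computed and summarized by treatment group". No fasting condition is attached. The section then adds: "A separate analysis will be performed excluding patients with no fasting status".
- Section 16.2.3.2 (analysis): descriptive statistics by visit, followed by "A separate analysis will be done with excluding data with non-fasting status". The MMRM comes next, with the primary model's terms, the baseline value as covariate and no imputation. It too has no fasting condition.

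Three general rules also bear on the point. Section 7.2 takes as baseline the last non-missing measurement before randomized treatment. Section 7.3 uses the earliest measurement when a test is repeated under the same visit number in by-visit summaries. Section 7.3 also lets unscheduled values fill a missing scheduled visit and maps early-termination FPG to the next planned visit. None of these rules looks at fasting status. Section 4.3 of the SAP declares no changes from the protocol's analysis.

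**The concern.** Because the exclusion of non-fasting samples is set apart as a separate analysis, the main analysis must keep them. A non-fasting value reflects recent food and mealtime insulin as well as the basal insulin under comparison, so it does not measure the named endpoint. A non-fasting Visit 6 sample has a wider reach than one at a later visit: it enters every later change for that subject and also the model covariate. If a site notices a non-fasting draw and repeats it fasting under the same visit number, the retest rule keeps the first value in the by-visit summaries.

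The fasting-only analysis could show whether this matters, but it has two definitions. Two programmers working from the two sections could deliver different data sets, and the choice between them could be made after results are seen.

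**Working it through.** The plan states no figure on this point: no non-fasting rate, no definition of fasting, and no standard deviation for FPG. The check is therefore a comparison of the two texts, then an illustration with assumed rates.

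**The two rules side by side**

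| | SAP 16.2.1.1 | SAP 16.2.3.2 |
|---|---|---|
| Unit removed | patient | data |
| Condition | no fasting status (not fasting, or possibly status not recorded) | non-fasting status |
| Reach | not stated | placed after the descriptive statistics; whether it also covers the MMRM is not stated |

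**Inputs for the illustration**

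- Five analysed samples per subject: baseline and Weeks 2, 6, 12 and 18 (SAP 16.2.1.1).
- 202 subjects planned (Protocol 7.1), used only to turn percentages into counts. All subjects are taken to have all five samples.
- Probability p that a sample is non-fasting: assumed 2%, 5% or 10%, independent between samples.

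**Formulas**

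- Literal patient rule, where any non-fasting sample removes the subject: 1 − (1 − p)^5.
- Value rule, upper end, where the Week 18 change is lost if either baseline or Week 18 is non-fasting: 1 − (1 − p)^2.
- Value rule, lower end, where an earlier fasting value replaces a non-fasting baseline, so only a non-fasting Week 18 sample loses the change: p.

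| p | Patient rule: subjects lost | Value rule, upper end: Week 18 changes lost | Value rule, lower end |
|---|---|---|---|
| 2% | 1 − 0.98^5 = 9.6% (about 19) | 1 − 0.98^2 = 4.0% (about 8) | 2% (about 4) |
| 5% | 1 − 0.95^5 = 22.6% (about 46) | 1 − 0.95^2 = 9.8% (about 20) | 5% (about 10) |
| 10% | 1 − 0.90^5 = 41.0% (about 83) | 1 − 0.90^2 = 19.0% (about 38) | 10% (about 20) |

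Against the upper end, the patient rule removes 2.2 to 2.4 times as many subjects from the Week 18 comparison (41.0/19.0 = 2.2; 9.6/4.0 = 2.4). Independence drives this gap. If non-fasting samples all came from the same subjects, any non-fasting sample would mark a subject whose samples are all non-fasting, and both rules would lose the fraction p.

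**Baseline.** The MMRM uses baseline both in the change score and as a covariate, so a subject with no baseline drops out of the model. Setting a non-fasting Visit 6 value to missing does not have to cause that. FPG is also drawn at Visits 1, 2 and 4 (schedule of events), and section 7.2 would then take the latest earlier value. That value must itself be fasting, and it comes from before or during run-in titration.

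**The case against.** The strongest reply is that both analyses are already pre-specified, so the point is about which one is called main. FPG has no margin, no success rule and no place in a testing hierarchy, so the label decides no trial conclusion. The sentence in section 16.2.1.1 may be loose wording for patients not fasting at a given visit, which would make it the same rule as in section 16.2.3.2. The rates above are assumed. Before-breakfast self-monitored glucose, averaged over three days, is analysed at Weeks 6, 12 and 18, so another measure relevant to basal insulin exists.

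Most of this stands, and it limits the point. A reader might infer that the FPG endpoint is invalid as planned; the documents do not support that, because a fasting-only analysis is planned. A reader might infer that one non-fasting sample certainly removes a subject; that is the literal reading of section 16.2.1.1 but not the only one. A reader might also infer that added noise will pass for similarity. The SAP reports differences with 95% confidence intervals, which noise would visibly widen, and it sets no similarity criterion for FPG.

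The reply does not remove two facts: the analysis carrying the endpoint's name admits samples known to be non-fasting, and the two sections name different units for exclusion.

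**Conclusion.** The point holds for a secondary endpoint and should be corrected. That the main analysis includes non-fasting samples is a necessary reading of the separate-analysis wording, although the SAP does not say it outright. The mismatch between patients and data is on the page.

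The size cannot be determined from the documents. The percentages rest on assumed rates, independence between samples and, for the patient rule, the literal reading. If non-fasting samples are very rare, the numerical effect is small and only the contradiction remains. No distortion between arms is shown: the trial is double-blind, and nothing suggests that non-fasting draws differ by arm. The HbA1c primary analysis and its sample size are untouched.

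**What to change.** Amend SAP sections 16.2.1.1 and 16.2.3.2 before unblinding:

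1. Base the main FPG descriptive tables and the MMRM only on values with confirmed fasting status, and keep the all-samples analysis as sensitivity. Values with unknown status then fall outside the main analysis; say so.
2. In section 16.2.1.1, replace the exclusion of patients with an exclusion of non-fasting values, so that both sections state one rule.
3. State that a non-fasting Visit 6 value is not used as baseline, and that the section 7.2 rule then applies to the last earlier fasting value. Do not rely on the MMRM to absorb a missing baseline.
4. State that a fasting retest at the same visit replaces a non-fasting first draw, as an exception to section 7.3 for FPG.

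Both analyses are already planned, so the cost is a few sentences and minor programming. The downside is a few values fewer in the main analysis and, for some subjects, a baseline from an earlier visit, before or during run-in titration.
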